1.0 Purpose of the Investigation

1.1 Name of investigational device

SCS for Lower-Limb Amputations (SCS-LLA)

1.2 Intended use of the investigational device

In the proposed study, we will investigate the efficacy of community use and safety of a neuroprosthetic system that uses spinal cord stimulation to restore sensory feedback after lower-limb amputation. The device will consist of an external data acquisition and stimulation system (Nomad Research System, Ripple LLC, Salt Lake City, UT) connected to 1-3 percutaneously inserted spinal cord stimulation (SCS) leads which have prior premarket clearance and approval (Abbott Medical Spinal Cord Stimulation (SCS) System, 510(k) K960728 and PMA P010032), see the attached Right of Reference letter, **Appendix A**) and a set of sensors mounted on the subject's prosthesis and limbs. Ongoing experiments in our lab have focused on the use of SCS to evoke sensations in the missing foot and shank after trans-tibial amputation. In those experiments, we used similar SCS leads to those that will be used in this study, percutaneously placed in the lateral lumbosacral epidural space for up to 29 days. All experiments to date have been deemed "Non-Significant Risk" by the University of Pittsburgh Institutional Review Board and performed under their approval. During those experiments, the external connector from the percutaneous leads is attached to an external stimulator during in-lab testing in our facilities at the University of Pittsburgh. Currently no stimulation is performed outside of the lab or clinic environment. During the proposed study, we will perform similar experiments over an extended 90-day period, and will also provide subjects with a portable stimulation and data acquisition system that can be used outside the lab environment for up to two weeks. During this two-week portion of the 90-day trial, subjects will transition from supervised use of the system to unsupervised use in the home and community. While ongoing lab-based experiments have been informative for our understanding of the ability to evoke and control the perception of sensations in the missing limb, ultimately, the goal of development of a somatosensory neuroprosthesis is for the system to be used in the community. Such community use will provide us with insight into the effects of daily and extended use of the system on function (e.g. balance control and gait stability) and changes in phantom limb pain. The extended duration of the experiments will also allow us to collect substantially more data and to prepare for the week-long trial of community use than can currently be achieved during the 29-day testing period.

1.3 Objectives of the clinical investigation

The proposed clinical investigation is a feasibility study directed toward the following aims:

Specific Aim 1: Demonstrate the safety of the SCS-LLA system over a period of up to 90 days. We will monitor adverse events throughout the study, and these results will provide supporting data for future studies with larger cohorts and a fully implanted SCS system.

Specific Aim 2: Characterize the sensations evoked by lumbar epidural spinal root stimulation in lower-limb amputees.

- **Specific Aim 2a:** Quantify the threshold (minimum charge and pulse rate) stimulus required to evoke sensory percepts and neurophysiological responses (e.g. reflexive EMG responses) during SCS, and monitor changes in those percepts and responses over time. These results will provide insight into the design requirements for a future SCS system, as well as a point of comparison among subjects and with other studies in the scientific literature. Additionally, the stability of the responses will provide insight into the feasibility of long-term use of the device.
- **Specific Aim 2b:** Evaluate the relationship between stimulation parameters (e.g. pulse width, pulse amplitude, stimulus location, etc.) and the modality and naturalness of perceived sensations. Lumbar SCS can evoke paresthesia referred to the amputated limb, but our goal is to produce meaningful (non-paresthetic) sensations. As we expect the stimulation parameters to have significant effects on the evoked sensations, we will perform standardized psychophysical examinations to determine the relationship between stimulation parameters and perceived sensations. These tests will be repeated at multiple points throughout the study to observe any changes that occur over multiple days of use.
- **Specific Aim 2c:** Document the subjective perception of lower-limb amputees of lumbar SCS for restoration of sensation. To achieve widespread adoption of a sensory neuroprosthesis, it will be crucial for amputees to perceive significant value from the device. As such, we will ask each subject to provide subjective feedback on their perceived utility of the sensory feedback provided by the device.

Specific Aim 3: Characterize the effects of lumbar SCS on phantom limb sensations and phantom limb pain in lower-limb amputees. This aim is secondary to the primary study goals in Aims 1 and 2, and as such, we will not exclude individuals that do not experience phantom limb pain.

- **Specific Aim 3a:** Document changes in phantom limb sensation during and shortly after lumbar SCS in amputees. Before placement of the spinal cord stimulator leads, we will document the subject's description of their perceived phantom limb. We will ask them to update their perception of the limb periodically throughout each experimental session, as well as within a month after the device has been removed.
- **Specific Aim 3b:** Document changes in phantom limb pain during and shortly after lumbar SCS in amputees. Before placement of the SCS leads, we will ask subjects about their history of perceived phantom limb pain. We will ask them to update their pain level periodically throughout each experimental session, as well as within a month after the device has been removed.

Specific Aim 4: Characterize the patterns of reflexive muscle activity that are evoked by SCS. Reflexive muscle activity plays a crucial role in maintaining standing balance and transitioning between phases of the gait cycle. As such, restoration of sensation may play an important role in restoring these functions. Importantly, these reflexes are context-dependent, and may change with posture.

Specific Aim 5: Characterize changes in control of a prosthetic limb in the presence of sensory feedback. The long-term goal of this line of research is to provide sensory feedback that can be used in the control of a prosthesis. In this study, we will test the subject's ability to stand and walk with and without sensory feedback provided by SCS. Using either a virtual prosthetic limb or an instrumented prosthesis, SCS will be modulated based on signals recorded from the limb

such as pressure under the foot or joint angles. In both the presence and absence of stimulation, subjects will be asked to perform tasks such as standing quietly and walking. We will perform a battery of clinically validated balance and gait metrics to evaluate the effects of sensory feedback on control of the prosthesis.

Specific Aim 6: Explore how sensations, balance, gait, and pain change after subjects have used the system in the community for up to two weeks. While lab-based studies will provide insight into the types of sensations and reflexive responses that can be evoked by SCS, as well as the impact of those sensations on balance control and gait stability, subjects' exposure to the device will be limited to tens of hours over the duration of the study. This limited access will restrict subjects' ability to learn to use the device and to incorporate sensory feedback into activities of daily living. Additionally, the effects on PLP may require an extended presentation of stimulation. We will perform detailed evaluations of the effects of sensory restoration in these subjects, monitor any changes in PLP and evoked reflexive activity, and track the extent of their use of the device during up to two weeks of community use, including up to one week of unsupervised use.

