2.4.2 Experimental procedures

Pre-surgical procedures and device placement will occur within 6 months after the subject undergoes screening procedures. We will work with each individual to determine the optimal testing schedule. The schedule will be designed to meet study goals and complete specific study tasks which will change over the duration of the study. The participant's engagement and training preferences will also be considered in this process. We will photograph or videotape portions of the experimental session. Appropriate permission will be obtained as needed for any photographs or videotaping of participants. Female participants will be encouraged to avoid getting pregnant throughout the duration of the research study. Experimental procedures are described below.

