Immediately following lead placement and up to 5 times per week for the following 90 days, experimental procedures will be performed. The day-to-day experimental procedures for each session will ultimately be decided by the PI, as they may depend on a variety of factors including progress towards our experimental goals, the current state of our technical setup (e.g. if hardware breaks and must be repaired), and the number of hours the subject is available on a given day. A typical day of testing might include psychophysical examination of sensations (e.g. receptive field mapping, measurement of threshold and just-noticeable difference) in the morning, followed by a lunch break, followed by x-rays and testing of the control of the prosthesis with sensory stimulation in the afternoon. Each testing session will be limited to no more than 8 hours, and will include breaks. Meals will also be provided. During experiments, SCS stimulation will either be delivered by an Abbott external stimulator or a current-controlled 32-channel neural stimulator (manufactured by Ripple, LLC; refer to **Section E** of this application for more detail).

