2.4.2.15 Weekly clinical exams and infection monitoring

Subjects will have clinical exams, in-person or via telemedicine visits, at least weekly following lead placement to monitor signs of infection. Physicians will verify that subjects do not have a fever, new redness at the incision site, or other signs indicative of infection. The physician will also ask if there have been any changes in medications. If local infection is suspected during a weekly exam, the examining physician will request drawn blood work (complete metabolic panel, C-reactive protein, erythrocyte sedimentation rate, complete blood count), swab the incision sites for culture, and schedule an additional clinical exam within 24 hours. A course of 5 to 7 day oral antibiotics will also be administered if superficial infection is suspected. Any signs of systemic infection (leukocytosis greater than $12 \times 10^9/L$, fever, or positive blood cultures) or the presence of local infection with discharge suspicious for infection will result in immediate removal of leads at the infected site and administration of intravenous antibiotics recommended by Infectious Disease clinicians. Any local infections that do not show improvement with a course of antibiotics within 3 days will also result in lead removal. Infectious Disease will be consulted at all signs of infection and study physicians will follow all Infectious Disease directives.

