2.4.2.26 Community use of SCS-LLA system

Subjects may participate in up to two weeks of community use of the SCS-LLA system and sensors applied to the exterior of their own prosthetic limb, including up to one week of unsupervised community use. Initially, during a period lasting no more than two weeks, subjects will engage in supervised community use of the system to gain experience with its operation and understanding of how to don/doff the system and how to respond to error conditions. After successfully completing clinic-based prosthetics training and assessment (Section 2.4.2.23) and technical training and assessment (Section 2.4.2.24), subjects will be cleared to participate in up to one week of unsupervised community use of the system. The total duration of supervised and unsupervised community use will not last longer than two weeks. During community use of the SCS-LLA system, data will be automatically collected by the external system. These data may include, but are not limited to, time of use, system state and error information, button presses, all sensor signals recorded by the system, and the timing and amplitude of all stimulation pulses delivered by the system. All data will be stored in a password protected file system inside the portable stimulation system (See Section E for more information). During the community use trial, subjects may also participate in lab-based testing such as balance and gait assessment, measurement of phantom limb pain, or sensory psychophysics.

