With respect to Specific Aim 2b, the results will produce descriptive anatomical maps of the modalities and locations of sensory percepts evoked by spinal root stimulation. These maps will allow us to examine the specificity of stimulation through individual electrodes as well as the overall coverage of the evoked sensory percepts across the entire amputated limb. The results of Specific Aim 2c will be a set of purely descriptive statements made by the subjects that will provide additional insight into their experience with SCS and their preferences for this type of neuroprosthetic intervention.

The results of Specific Aims 3a and 3b will be a combination of descriptive statements on the subjective experience of SCS and its effects on phantom limb sensations and pain, as well as a data set including perceived pain ratings from a visual analog scale at multiple time points before and during the experimental study. These pain-rating results will be

compared within each subject and across subjects via regression analysis to determine if there is any effect of spinal root stimulation on phantom pain levels.

The results of Specific Aims 4 and 5 will be a data set including EMG, kinematics, and performance metrics that will allow us to quantify the subject's ability to control a prosthetic limb with and without sensory stimulation. Kinematic and performance metrics data will be compared within and across subjects using regression analysis to quantify changes in control with the addition of sensory stimulation.

With respect to Specific Aim 6, we will utilize analysis of variance to compare balance, gait, and pain scores before and after the trial of community use.

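### While the leads are in, phantom-pain VAS ratings exist only where lab sessions happen to fall, so their number and timing are uncontrolled and the community-use weeks may have none

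*Combined protocol and SAP*

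**What the plan says.** **When pain is rated.** Section 1.3, Aim 3b, starts before implantation: "Before placement of the SCS leads, we will ask subjects about their history of perceived phantom limb pain". For the implanted period it says "We will ask them to update their pain level periodically throughout each experimental session", and it adds an update "as well as within a month after the device has been removed". Section 2.4.2.20 likewise places the 0-10 VAS periodically within experimental sessions. It schedules the pain portion of the Trinity scales and the McGill questionnaire before placement, at least once in the 90 days, and within a month after removal.

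**When sessions occur.** The end of section 2.4.2.11 allows sessions up to five times a week for 90 days and states no minimum. Section 2.4.2 builds the schedule individually around study goals and tasks, and then adds: "The participant's engagement and training preferences will also be considered in this process". The content of each session is the investigator's decision, and one listed factor is "the number of hours the subject is available on a given day".

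**Community use.** Section 1.3, Aim 6, suggests that an effect on phantom pain may need longer stimulation than lab sessions give, and says that changes will be monitored. Section 2.4.2.26 says only that "subjects may also participate in lab-based testing such as balance and gait assessment, measurement of phantom limb pain, or sensory psychophysics".

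**Analysis.** Section 2.5.4 describes how the pain ratings are to be handled: "compared within each subject and across subjects via regression analysis to determine if there is any effect of spinal root stimulation". It also says that single-subject analyses will be used, and that pain scores before and after community use will be compared by analysis of variance.

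**A contact that does not depend on sessions.** Section 2.4.2.15 states: "Subjects will have clinical exams, in-person or via telemedicine visits, at least weekly following lead placement to monitor signs of infection". The exam covers infection signs and medication changes. No pain score is listed.

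**The concern.** An outcome measured only when a subject attends is sampled on a schedule that may itself be related to the outcome. Here three things are left open together: how many VAS ratings each subject gives, on which days, and how the across-subject regression treats unequal numbers.

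The link to pain is not far-fetched. Section 2.5.2 foresees subjects withdrawing because of worsening pain, and such subjects would stop contributing ratings early. A subject who reschedules on a bad day leaves that day unrated.

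The community-use weeks matter most. They are the period in which the plan itself thinks a pain effect might appear, yet nothing requires a rating there. The Trinity and McGill assessment during implantation is not tied to that period either, so it need not fall near it. Ratings that are not taken while the leads are in cannot be recovered afterwards.

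**Working it through.** The plan gives no figure to reproduce. Section 2.5.3 justifies the sample size by feasibility alone, without a power calculation. The steps below separate what follows from the text from what is assumed.

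**1. From the documents**

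- Maximum sessions per subject: 5 × 90/7 = 64.3, so about 64. Minimum: not stated.
- Share of the implanted period in community use: up to 14/90 = 16%, of which unsupervised up to 7/90 = 8%. Required pain ratings in that window: none.
- Clinical exams at least weekly: 90/7 = 12.9, so about 12 or 13 per subject over a full 90 days, whatever the session schedule.

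**2. Unequal numbers of ratings (assumed attendance and effects)**

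Assume ten subjects (the target in section 2.3.2), one rating per session, and a regression that pools ratings without regard to subject. Three subjects attend five sessions a week, and seven attend m a week. The share of ratings from the three is 15/(15 + 7m). The Kish effective number of subjects is (Σw)²/Σw², which here is (15 + 7m)²/(75 + 7m²). If the three changed by -2 VAS points and the other seven by 0, the pooled mean change is -2 × share. With equal weight per subject it is -2 × 3/10 = -0.60.

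| m per week | Share from the three | Effective subjects | Pooled mean change |
|---|---|---|---|
| 1 | 15/22 = 68% | 5.9 | -1.36 |
| 2 | 15/29 = 52% | 8.2 | -1.03 |
| 3 | 15/36 = 42% | 9.4 | -0.83 |
| 5 | 15/50 = 30% | 10.0 | -0.60 |

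With equal attendance (last row) the distortion disappears. If the effects were assigned the other way round, so that frequent attenders changed least, the pooled figure would be too small instead of too large.

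**3. Attendance that depends on pain (assumed)**

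Let b be the share of bad-pain days, q the attendance on those days relative to other days, and d the extra pain on them. The shift in the observed mean is d × [bq/(bq + 1 - b) - b]. With d = 3:

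- b = 0.10, q = 0.75: 3 × (0.077 - 0.10) = -0.07 points.
- b = 0.20, q = 0.50: 3 × (0.111 - 0.20) = -0.27 points.
- b = 0.30, q = 0.25: 3 × (0.097 - 0.30) = -0.61 points.

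These are shifts in mean pain over the implanted period relative to all days. They are not biases in change from baseline. If baseline ratings were also taken only on days the subject could attend, some or all of the shift would cancel.

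**The case against.** Several stronger statements are tempting, and the documents do not bear them out.

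- **That pain is rated only in lab sessions.** This is true of the VAS while the leads are in, but not of the study. Aim 3b covers pain history before placement and an update after removal, section 2.4.2.20 adds questionnaires before, during and after, and section 2.4.2.28 adds contacts within 48 hours and within one month of removal.
- **That attendance follows engagement.** Engagement is one consideration beside study goals. The remark about available hours concerns what is done in a session, not whether one takes place. Section 2.5.2 also lists failure to attend sessions among possible reasons for lead removal, so regular attendance is expected even though no number is given.
- **That engaged subjects will dominate the regression.** This needs both markedly unequal attendance and a pooled model. Section 2.5.4 neither specifies nor excludes such a model, and its single-subject approach would avoid the weighting problem within subjects. Selective timing within a subject would remain.
- **That the result will lean towards pain relief.** The direction is unknown. For most of the study stimulation is available only in sessions, so subjects with worse pain might attend more. In the weighting example the subject-level changes are taken as real, so unequal weights distort their average without creating an effect.
- **That community use has no pain data.** Measurement there is permitted and Aim 6 intends monitoring. A before/after comparison does not strictly need ratings inside the period.

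It is also fair that this is a descriptive feasibility study with Aim 3 expressly secondary, and that the pain endpoint in section 2.5.1 is a McGill change, not the VAS.

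All of this limits the size of the point. It does not supply a minimum number of ratings, a rating calendar, a required rating during community use, or a stated treatment of unequal numbers.

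**Conclusion.** The point holds in a limited form. During implantation the VAS is tied to sessions that have a cap but no minimum and no fixed timing. The number and dates of ratings can differ between subjects and may depend on pain. The community-use weeks, up to 16% of the implanted period and the focus of Aim 6, may hold no rating. The across-subject analysis does not say how unequal numbers will be handled.

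Neither the direction nor the size of any bias can be established from the documents. The pooled shares of 42% to 68% and the shifts of 0.07 to 0.61 VAS points show what is possible under assumed attendance, effects and a pooled model. They are not predictions. A reader should not infer that the plan is built to show pain relief, or that its safety or efficacy endpoints are compromised. The primary endpoints do not use these ratings, and the secondary pain endpoint uses the McGill questionnaire. The change is worth making because it costs little and the missing data could not be collected later.

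**What to change.** **Section 2.4.2.20.** Add a 0-10 VAS phantom-pain rating at each clinical exam already required at least weekly by section 2.4.2.15, by telemedicine where that is how the exam is held, and state that this includes the community-use weeks.

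**Section 2.5.4.** Analyse this weekly series alongside the in-session ratings. Keep the in-session ratings in the Aim 3 result, because they measure pain during stimulation, which Aim 3b sets out to document. For across-subject analyses, name the subject as the unit: either per-subject summaries with equal weight, or a repeated-measures model with a subject effect. Report the number of ratings per subject from each source.

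**Cost.** One extra question at about 12 or 13 existing exams per subject, a short wording change in two sections, and slightly more analysis. No new visits or staff are needed.
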